Hypothesis 0b (H0b): There is no difference in pain between the control group and the study groups when comparing the routine Hepatitis B vaccination with the tap method applied during Hepatitis B vaccination in infants.

Hypothesis 1b (H1b): There is a difference in pain between the control group and the study groups in infants during routine Hepatitis B vaccination and during Hepatitis B vaccination administered using the finger-prick method.

Method

Type of Research

The research is planned to be conducted as a randomized controlled trial to examine the analgesic and physiological effects of mechanical vibration and fiske methods in infant vaccinations.

Location and Timing of the Research

Research data will be collected at Gümüşhane Kelkit No. 1 ASM. According to the study schedule, ethical committee and institutional approval will be obtained before starting the research, following the submission and acceptance of the thesis proposal, and then the data collection process will begin. Data collection, obtaining expert opinions, and data entry will take place over a 12-month period. Data analysis and thesis report writing will be completed within a three-month period, and the research is expected to be carried out according to the planned schedule.

Ethical Aspects of the Study

Before starting the study, the necessary permissions will be obtained from the Scientific Research Ethics Committee of Karadeniz Technical University Health Sciences. After obtaining permission from the ethics committee, institutional permission will be obtained from the Gümüşhane Provincial Health Directorate, to which Gümüşhane Kelkit No. 1 ASM is affiliated, in order to carry out the study. All parents of newborn babies included in the study will be informed about the purpose, type, implementation process, and content of the study, the purpose for which the video images taken during the data collection process will be used, the fact that all data will be stored on the researcher's personal computer, and where the obtained data will be used. Verbal and written consent will be obtained from the parents.

Study Population and Sample

The study population will include infants whose mothers, who agreed to participate in the study, applied for the second dose of the Hepatitis B vaccine at the end of the first month as part of routine preventive care at Gümüşhane Kelkit No. 1 ASM and who met the inclusion criteria for the study.

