A power analysis was performed to select the patients to be sampled. The G*Power 3.1.9 program was used to calculate the number of participants to be included in the study. During the calculation, the effect size was taken as 0.31 based on Kanbur's (2021) study for the parameters specified according to the type of test, the margin of error was taken as 0.05, the power value was taken as 0.80, the number of groups was taken as 3, and the number of measurements was taken as 3. The calculation resulted in a minimum participant number of 72. Accordingly, it was planned to include a minimum of 24 participants in each group (27).

Research Inclusion Criteria

The parent agrees to participate in the study/volunteers to participate,

The gestational age is between 38 and 42 weeks,

The birth weight is between 2500 g and 4000 g,

No pain medication is administered prior to vaccination,

Body temperature is within normal limits,

Exclusion Criteria

Parents who do not consent to participate in the study,

Gestational age below 38 weeks or above 42 weeks,

Infants with congenital diseases or birth defects will not be included in the study.

Data Collection Tools

Newborn Baby Identification Form

The newborn infant information form created by the researcher consists of a total of nine questions, including the infant's group number, gender, gestational age, mode of delivery, birth weight and length at birth, postnatal age, current weight and height, and feeding method (27, 29).

Parent Information Form

The parent information form created by the researcher consists of a total of six questions, including the parent's group number, mother and father's ages, education status, and occupation information (27).

Newborn Baby Observation Form

The observation form prepared by the researcher is a form on which physiological parameters will be recorded, including the baby's group, crying time with the start of the vaccination procedure, the baby's body temperature before and after the procedure, the baby's respiratory rate before and after the procedure, and oxygen saturation and heart rate before, during, and after the procedure. This information about the infant before, during, and after the procedure **will be observed by the researcher and recorded on this form (27, 29).**

Neonatal Infant Pain Scale (NIPS)

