Developed by Lawrence and colleagues, it is used to measure the behavioral responses to pain in preterm and term infants during the first six weeks after birth. The scale ensures that the infant's behavior, which is the first step in meeting the newborn's needs, is objectively assessed at the bedside. The scale's reliability coefficient has been found to be between 0.92 and 0.97. It is stated that the scale can be used reliably and can measure the effectiveness of the intervention, and six behaviors in response to pain are evaluated (27). Facial expression, breathing pattern, arm movements, leg movements, and alertness are scored as 0 or 1, while crying is scored as 0, 1, or 2. The total score ranges from 0 to 7, with a high score indicating severe pain. The Turkish adaptation of the scale was performed by Akdovan and Çiğdem in 1999 (28).

Application Tools

Mechanical Vibrator

The Norco NC70209 brand mini vibration device, which is lightweight, portable, and battery-operated, with silicone heads for small areas, vibrates at 5500 rpm and is intended for use on infants in the mechanical vibration group.

Video Camera

The digital camera of the Samsung Galaxy M31 phone is planned to be used to determine pain levels before, during, and after the Hepatitis B vaccination procedure in infants, to evaluate physiological parameters, to accurately calculate crying times, and to check for inter-observer agreement in the evaluation of pain scores. The camera has an 8-megapixel video resolution and features that allow images to be reviewed on a wide screen.

Pulse Oximeter

An ACCURATE handheld rechargeable pulse oximeter device is planned to be used at the patient's bedside to easily view measurement trends on the screen for determining oxygen saturation and heart rate in infants. The device is designed to monitor pulse and blood oxygen levels in premature infants, newborns, children, and adults. Values can be tracked by attaching it to the adjustable wrist, ankle, or finger.

Thermometer

A KANGJI brand, model GQ-129, non-contact infrared digital screen thermometer is planned to be used to measure the body temperature of infants. Body temperature measurement will be taken from the forehead, and the thermometer will be held 3-5 cm away from the infant's forehead.

Data Analysis

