IBM SPSS 27 software will be used to analyze the data in this study. Continuous data will be presented as mean \pm standard deviation, while categorical data will be presented as frequency and percentage. If the values obtained from the measurements taken for each variable throughout the study show a normal distribution, the parametric test ANOVA test will be used to compare repeated measurement results. If the values do not show a normal distribution, the non-parametric Friedman test will be used. For intergroup analyses, the parametric test, one-way ANOVA, will be used for those showing a normal distribution, and the non-parametric test, Kruskal Wallis H test, will be used for those not showing a normal distribution. Statistical significance will be accepted as $p < 0.05$ for all analyses.

Research

1. Güven SD, Çakırer Çalbayram N (2023). The effect of Helper skin tap technique on hepatitis B vaccine intramuscular injection pain in neonates: A randomized controlled trial. *Explore* 19(2): 238-242.

4. Türk Dil Kurumu (2023). Türk Dil Kurumu Sözlükleri [online]. Erişim adresi: <https://sozluk.gov.tr/>. [Erişim tarihi: 15.12.2023].

6. Cwynar CM Osborne K (2019). Immunization-Associated Pain: Taking Research to the Bedside. *Journal of Pediatric Health Care* 33(4): 446-454.

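### The before-procedure values of pain and four vital signs are collected but not used by the named between-group tests; adjusting for them is an optional, nearly free gain in precision of unknown size

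*Combined protocol and SAP*

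**What the plan says.** Five outcomes have a value from before the injection.

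- **Heart rate and oxygen saturation:** the Newborn Baby Observation Form lists "oxygen saturation and heart rate before, during, and after the procedure".
- **Respiratory rate and temperature:** the same form lists "the baby's respiratory rate before and after the procedure", and temperature likewise.
- **Pain:** under Application Tools, the video is to be used to "determine pain levels before, during, and after the Hepatitis B vaccination procedure in infants".

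Crying time has no before value and is outside this point.

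The Data Analysis section states: "For intergroup analyses, the parametric test, one-way ANOVA, will be used for those showing a normal distribution", with Kruskal-Wallis otherwise. A separate sentence gives ANOVA or Friedman for repeated measurements and names no group factor. No covariate, change score or other baseline-adjusted comparison appears.

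Under Study Population and Sample, the sample size assumes three groups, and "the number of measurements was taken as 3". Under Type of Research, the trial is to "examine the analgesic and physiological effects of mechanical vibration and fiske methods in infant vaccinations", although the stated hypotheses concern pain alone.

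**The concern.** One-way ANOVA and Kruskal-Wallis compare the values at one time point and ignore how each infant stood beforehand. Where infants differ stably from one another, that variation stays in the error term although the plan has already paid to measure it. The planned minimum is 24 infants per arm, so precision is limited, and physiological effects are a stated purpose.

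A second matter is at stake. The plan does not say how the before values enter the group comparison. The choice among raw values, changes and adjusted values could therefore be made after the data are seen.

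**Working it through.** **1. The plan's own figure.** Inputs from Study Population and Sample: effect size 0.31 (taken here as Cohen's f, since the metric is not named), alpha 0.05, power 0.80, 3 groups, 3 measurements, N = 72. For the between-groups test in a repeated-measures ANOVA, the noncentrality is λ = f²·N·m / (1 + (m − 1)ρ), with 2 and N − 3 degrees of freedom. The correlation ρ is not stated; 0.5 is assumed.

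λ = 0.0961 × 72 × 3 / 2 = 10.38, which gives power 0.813. N = 69 gives 0.794. So 72 is reproduced under that assumption. It is not the test that the Data Analysis section names for group comparisons. One-way ANOVA at a single time point has λ = 0.0961 × 72 = 6.92 and power 0.630.

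**2. Precision with and without the before value.** This needs no effect size. Take one arm against control, 24 per arm, in units of the outcome SD.

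- Unadjusted: t(0.975; 69) × √(2/24) = 1.9949 × 0.2887 = 0.576.
- ANCOVA with ordinary standard errors: t(0.975; 68) × √[(2/24)(1 − r²)(1 + 1/67)]. The last factor is the expected cost of chance imbalance in the before value. At r = 0 this is 1.9955 × 0.2887 × 1.0074 = 0.580.

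| r (assumed) | Adjusted half-width | Change from 0.576 |
|---|---|---|
| 0 | 0.580 | +0.8% |
| 0.2 | 0.569 | −1.3% |
| 0.3 | 0.554 | −3.9% |
| 0.5 | 0.503 | −12.7% |
| 0.7 | 0.414 | −28.0% |

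Setting the two expressions equal gives r = 0.123 as the break-even.

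**3. The same range as power.** For a single time point with f = 0.31 and N = 72, λ = 6.92/(1 − r²) with 2 and 68 degrees of freedom. Power is 0.629, 0.648, 0.673, 0.762 and 0.907 at r = 0, 0.2, 0.3, 0.5 and 0.7, against 0.630 unadjusted. This formula leaves out the small imbalance factor used in step 2.

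**4. Which measures could gain.**

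- **Heart rate and respiratory rate:** stable differences between infants are plausible. This is an inference, because the documents give no data.
- **Temperature:** the inclusion criterion "Body temperature is within normal limits" narrows the before values. If it kept the central 90% of them (assumed), r = 0.50 would fall to 0.41.
- **Oxygen saturation:** it cannot exceed 100%, which may limit r.
- **NIPS:** "The total score ranges from 0 to 7, with a high score indicating severe pain", and calm infants may score zero beforehand. In a simulation with invented inputs (during-procedure mean 4.5, SD 1.8, underlying correlation 0.5, f = 0.31, 80% of infants at zero beforehand), power moved from 0.61 to 0.65 and the half-width from 0.97 to 0.93 points. At 90% and 95% zeros, computed with HC3 robust errors, power was 0.62 and 0.60: practically no gain.

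**5. Sparse NIPS scores.** If 95% of infants score zero beforehand, the chance that none of 72 scores above zero is 0.95⁷² = 2.5%, and the slope cannot then be estimated. The chance of exactly one is 72 × 0.05 × 0.95⁷¹ = 9.4%, and the slope then rests on one infant. A fallback is needed.

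**The case against.** **A group-by-time analysis may have been intended.** The sample size uses three measurements, and in such a model the before value is already present. This is a fair reading of the sample-size paragraph, but the Data Analysis section does not name that analysis. It would also treat the before value as an outcome level, not a covariate. Comparing changes from before has relative variance 2(1 − r), against 1 − r² for ANCOVA. The difference is (1 − r)², so the change is never the more precise. The mismatch between the sizing test and the named test is a separate matter, and ANCOVA does not settle it or re-justify 72.

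**The gain is least where the hypotheses lie.** This stands. For NIPS it may be nil, and the case rests mainly on heart rate and respiratory rate.

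**The covariate may not be a true baseline.** Under Aim, tapping comes before the injection, and no section says whether the before values precede tapping or vibration. This also stands, and it makes the fix conditional.

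**Stronger readings.** A reader might infer that the unadjusted comparisons are biased; randomization keeps them valid. A reader might infer that adjustment must come with robust (HC3) errors for every measure. Simulations do not support that: ordinary-error ANCOVA held its size at 0.048 to 0.054 for normal and NIPS-type data, with intervals about 2–3% narrower. Blanket HC3 would raise the break-even r from about 0.12 to about 0.25.

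**Conclusion.** The point holds as an optional efficiency and pre-specification improvement. The before values are collected for five outcomes, and the named between-group tests do not use them. At 24 per arm, adjustment changes the half-width by anything from a loss of 0.8% (r = 0) to a gain of 28% (r = 0.7), with break-even near r = 0.12.

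The result assumes a roughly linear relation between the before value and the outcome, similar variances across arms, and a covariate taken before any intervention. A reader might take the power of 0.762 at r = 0.5 as what the trial would achieve for pain. The documents do not support that: they give no r for any measure, and the assumed 0.5 that reproduces 72 is not evidence of one.

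**What to change.** In Data Analysis, state that:

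- each during and after value of heart rate and oxygen saturation, and each after value of temperature and respiratory rate, will be compared between groups by ANCOVA on group plus the infant's own before value, with ordinary standard errors;
- adjusted differences from control will be reported with 95% confidence intervals;
- Kruskal-Wallis on the post-baseline values will be a sensitivity analysis;
- NIPS will be handled in the same way unless too few infants have a before score above zero to estimate the slope, in which case it will be compared without the covariate.

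Fix that minimum number in advance. Fewer than 5 in the whole sample is one possible rule, though the number is a judgement. With 72 infants it would be triggered in under 0.1%, 14% and 71% of trials if 80%, 90% and 95% score zero beforehand.

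In the Newborn Baby Observation Form section, and for the video-scored pain value, state that the covariate is the value recorded before any tapping or vibration begins. Leave a measure unadjusted if that cannot be assured.

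Cost: one error degree of freedom (68 instead of 69) and a few sentences. No extra infants or measurements are needed. If r is zero, the interval widens by under 1%.

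### Body temperature and respiratory rate are read only twice, so the stated Friedman fallback becomes the sign test and usually loses power; a signed-rank test should be named for these two variables

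*Combined protocol and SAP*

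**What the plan says.** The Data Analysis section sets a single rule for change over time. It opens with "If the values obtained from the measurements taken for each variable throughout the study show a normal distribution", in which case ANOVA is used for the repeated measurements; otherwise, "If the values do not show a normal distribution, the non-parametric Friedman test will be used". The rule does not depend on how many readings a variable has, and no paired two-sample test (paired t or Wilcoxon signed-rank) is named. Comparisons between groups are handled separately, by one-way ANOVA or Kruskal-Wallis.

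The number of readings differs by variable:

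- Newborn Baby Observation Form, two readings: "the baby's body temperature before and after the procedure" and "the baby's respiratory rate before and after the procedure".
- Same form, three readings: "oxygen saturation and heart rate before, during, and after the procedure".
- Video Camera section, three readings for pain: the recording is used "to determine pain levels before, during, and after the Hepatitis B vaccination procedure in infants".

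**The concern.** Friedman ranks the readings within each infant. With three readings this keeps useful information on the pattern over time. With two, each infant contributes only a rise, a fall or a tie, so a fall of 1 breath per minute counts the same as a fall of 15. Read as written, a non-normal temperature or respiratory rate goes to exactly this test.

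At stake is sensitivity. A real before-after shift in either variable could be missed by the planned test and found in the same data by a test that also uses the size of the change. If no two-reading test is named in advance, the choice may also end up being made after the data have been seen.

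**Working it through.** **The plan's own figure.** The Study Population and Sample section gives a minimum of 72 (24 per group) from effect size 0.31, alpha 0.05, power 0.80, 3 groups and 3 measurements. Reading 0.31 as Cohen's f and assuming a correlation of 0.5 between measurements (not stated in the plan), the between-factors repeated-measures ANOVA has

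λ = f²·N·m / (1 + (m − 1)ρ) = 0.31² × 72 × 3 / (1 + 2 × 0.5) = 20.76 / 2 = 10.38,

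with 2 and 69 degrees of freedom. Power is 0.813, and 72 is the smallest multiple of 3 that reaches 0.80. The figure reproduces. It concerns a comparison between groups, so the choice of a before-after test does not enter it.

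**Friedman with two readings.** Let n₊ and n₋ be the numbers of infants whose reading rises and falls. With k = 2 the tie-corrected Friedman statistic reduces to

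(n₊ − n₋)² / (n₊ + n₋),

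which is the sign-test statistic. The two agreed exactly in 500 of 500 simulated data sets with ties.

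**Power of the stated test.** Let d be the mean change divided by the SD of the changes. The documents give neither quantity, so d is an assumption. For normal differences the chance of a rise is Φ(d). Without ties, the chi-square cut-off of 3.84 is passed at n = 24 when 17 or more (or 7 or fewer) infants rise, and at n = 72 when 45 or more (or 27 or fewer) rise. Two examples:

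- n = 24, d = 0.6: Φ(0.6) = 0.726; the binomial probability of 17 or more, or 7 or fewer, out of 24 is 0.67.
- n = 72, d = 0.35: Φ(0.35) = 0.637; the binomial probability of 45 or more, or 27 or fewer, out of 72 is 0.63.

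**Comparison with signed-rank.** The plan does not say whether the before-after test is run within each group (n = 24) or on all infants (n = 72), so both are shown. The level is two-sided 0.05 (sidedness is not stated in the plan). The signed-rank figures are simulated.

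| n | d | Shape of differences | Friedman (sign) | Signed-rank |
|---|---|---|---|---|
| 24 | 0.3 | normal | 0.25 | 0.28 |
| 24 | 0.5 | normal | 0.53 | 0.63 |
| 24 | 0.6 | normal | 0.67 | 0.79 |
| 72 | 0.3 | normal | 0.50 | 0.69 |
| 72 | 0.35 | normal | 0.63 | 0.81 |
| 24 | 0.5 | uniform (light tails) | 0.34 | 0.58 |
| 24 | 0.5 | logistic | 0.62 | 0.68 |
| 24 | 0.5 | t, 3 df | 0.85 | 0.85 |
| 24 | 0.5 | Laplace | 0.78 | 0.75 |
| 72 | 0.3 | logistic | 0.61 | 0.75 |
| 72 | 0.3 | t, 3 df | 0.87 | 0.92 |
| 72 | 0.3 | Laplace | 0.84 | 0.84 |

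The asymptotic efficiency of sign against signed-rank under normal differences is 2/3, in line with the normal rows. The gap is widest for light tails, shrinks as tails get heavier, and vanishes or slightly reverses for Laplace differences.

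**The case against.** **The fallback applies only to non-normal data, where the sign test can do well.** This stands in part. A reader might infer that the stated rule always loses power; the Laplace and t (3 df) rows show that it does not. But the plan checks the normality of the values, not of the paired differences. Skewed readings can give differences without heavy tails, and for skewed readings the simulated powers were 0.62 versus 0.67 (n = 24, 0.6 SD) and 0.66 versus 0.77 (n = 72, 0.35 SD). A loss is therefore the usual case.

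**Signed-rank has a cost.** This stands as a caveat. It tests the median change only if the differences are roughly symmetric. With strongly skewed differences of zero median (a shifted exponential) it rejected 12% of the time at n = 24 and 29% at n = 72, against 7% and 4% for the sign test. If instead there is no time effect at all, so that the two readings are exchangeable, the differences are symmetric and signed-rank keeps its size (about 0.05, even with skewed readings). The assumption needs stating, but it does not defeat the change.

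**Friedman on two readings is a legitimate test.** Agreed. A reader might go further and infer that its p-value is materially off-size here. The documents do not support that. Without ties the true size is 0.064 at n = 24 but 0.044 at n = 72; the plan does not say which n applies, and digital temperatures and counted breaths are likely to give zero differences, which change the figure.

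**It does not bear on what the trial tests.** Agreed. The main hypotheses concern pain, which has three readings, and they compare groups. The Aim mentions physiological parameters only in general; temperature and respiratory rate come from the observation form. A better before-after test for them says nothing about vibration or tapping against control.

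**Conclusion.** The point holds as a modest correction to the analysis plan. For the two variables with two readings, the only non-parametric repeated-measurement test stated is the sign test under another name. With normal differences it gives up about 10 points of power against signed-rank at n = 24 (changes of 0.5 to 0.6 SD) and about 18 points at n = 72 (changes of 0.3 to 0.35 SD). These sizes rest on assumed standardised changes, a two-sided 0.05 level and no ties; the documents supply no expected change or SD.

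The reach is limited to secondary within-infant comparisons. A reader might infer that the trial's power or its main conclusions are weakened. They are not: the pain hypotheses, the between-group tests and N = 72 do not depend on this rule.

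**What to change.** In the Data Analysis section, limit Friedman to the outcomes with three readings (NIPS, heart rate, oxygen saturation). For body temperature and respiratory rate, state that when the after-minus-before differences are not normal, the Wilcoxon signed-rank test is applied to those differences. In the same place, say how tied and zero differences are handled, and that reading the result as a median change assumes roughly symmetric differences.

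The cost is a sentence or two, settled before analysis. Sample size, data collection and the between-group tests stay as they are. The one real trade-off is the symmetry assumption, which the sign test does not need. The change adds no comparison of the randomised groups and should not be presented as doing so.

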To minimize these adverse events, the American Academy of Pediatrics and the International Neuropsychiatric Pain Group recommend reducing pain in infants and using non-pharmacological pain relief methods as the primary option in newborns (18, 19). Studies indicate that non-pharmacological tactile stimuli such as vibration may have the potential to reduce pain due to the presence of numerous large fibers in the skin (11, 20-22). Infants are exposed to mechanical vibration through vibrating infant seats or swings to calm them in both hospital and home settings (23). However, it is known that vibration applied with a mechanical hand vibrator is also used as a method of chest physiotherapy in Neonatal Intensive Care Units (NICUs) to calm colicky infants (24, 25).

It has been suggested that manipulations such as rubbing, applying pressure, and tapping directly on or below painful areas may also alleviate pain by releasing beta-endorphins into the bloodstream (13). It has been suggested that simple manual pressure applied to the injection site (similar in effect to the fiske method) may be a useful technique for reducing injection pain (7, 13, 26). The current literature shows that non-pharmacological mechanical vibration and fiske applications may be effective in reducing injection pain (7, 11).

Based on this information, the aim is to evaluate the effect of mechanical vibration and fiske tapping methods in reducing pain during vaccination in one-month-old infants receiving healthcare as part of routine primary preventive healthcare services.

Aim

This study aims to investigate the effect of tapping the injection site prior to the second dose of Hepatitis B vaccine administered to the anterior surface of the vastus lateralis muscle during infancy and the application of mechanical vibration to the injection site throughout the vaccination procedure on acute pain, crying duration, and physiological parameters that may occur due to intramuscular injection.

Research Hypotheses

Main Hypotheses

Hypothesis 0a (H0a): There is no difference in pain between the control group and the study groups when mechanical vibration is applied during Hepatitis B vaccination in infants compared to routine Hepatitis B vaccination.

Hypothesis 1a (H1a): There is a difference in pain between the control group and the study groups when mechanical vibration is applied during Hepatitis B vaccination in infants compared to routine Hepatitis B vaccination.

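### The two main hypotheses compare vibration and tapping separately with routine vaccination, but the only planned between-group tests are three-group omnibus tests, and no pain score is named as the deciding one

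*Combined protocol and SAP*

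**What the plan says.** Under Research Hypotheses, H1a reads "There is a difference in pain between the control group and the study groups when mechanical vibration is applied during Hepatitis B vaccination", set against routine vaccination. The second null, H0b, is framed as no difference "when comparing the routine Hepatitis B vaccination with the tap method applied during Hepatitis B vaccination in infants". Its alternative begins "There is a difference in pain between the control group and the study groups in infants during routine Hepatitis B vaccination" and then names a finger-prick method, which I read as the tap method because the paired null names tapping. Each pair therefore names one intervention and one comparator, although the wording refers to study groups in the plural.

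The Data Analysis section gives one between-group rule: "For intergroup analyses, the parametric test, one-way ANOVA, will be used for those showing a normal distribution", while the "Kruskal Wallis H test, will be used for those not showing a normal distribution". Repeated measurements are to be compared by ANOVA or, failing normality, by Friedman. The 0.05 level applies to every analysis. No contrast with control, follow-up test or rule covering the two hypotheses together is given.

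Under Video Camera, recordings serve "to determine pain levels before, during, and after the Hepatitis B vaccination procedure in infants". The paragraph before the Aim says "the aim is to evaluate the effect of mechanical vibration and fiske tapping methods in reducing pain during vaccination in one-month-old infants". That points towards the during-procedure score but does not designate it as primary.

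Study Population and Sample derives 72 infants, 24 per group, from an effect size of 0.31 and an error of 0.05, where "the power value was taken as 0.80, the number of groups was taken as 3, and the number of measurements was taken as 3".

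**The concern.** One-way ANOVA and Kruskal-Wallis ask whether all three groups are alike. Neither main hypothesis asks that. If the omnibus test is not significant, both nulls stand. If it is significant, the plan has no step that says whether vibration, tapping or both differ from routine vaccination. The omnibus test also responds to a difference between vibration and tapping, which neither hypothesis is about.

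The repeated-measurement sentence does not fill the gap. A group factor in that ANOVA would again be a three-group omnibus test, and Friedman makes no comparison between groups.

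The hypotheses fix which contrasts matter. The follow-up procedure and the deciding time point are left open, and both could be settled after results are known. What is at stake is whether the trial can support a separate claim for each method at a known error rate.

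**Working it through.** **Inputs.** From Study Population and Sample: effect size 0.31, alpha 0.05, power 0.80, 3 groups, 3 measurements, 24 per group. Assumed, because not stated: 0.31 is Cohen's f; correlation between measurements is 0.5; data are normal with a common SD.

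**1. The plan's own figure.** For the between-groups effect over m measurements, the noncentrality is λ = N f² m / (1 + (m − 1)ρ) = 72 × 0.0961 × 3 / 2 = 10.38. With 2 and 69 df the critical F is 3.13 and power is 0.813. The smallest N reaching 0.80 is 70, which becomes 72 with equal groups. So 72 is reproduced, but for a three-group omnibus test over three measurements. Other readings do not give it: within-factor 21, interaction 24, one-way ANOVA at one time point 105. Correlations from 0 to 0.8 give 39 to 90.

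**2. The omnibus test at one time point.** λ = 72 × 0.0961 = 6.92, so power is 0.63. This depends only on f, not on which group differs:
- One group shifted by d, or both shifted equally: the variance of the three means is 2d²/9, so d = 0.31 / √(2/9) = 0.658.
- Evenly spaced means with control at one end: the variance is d²/6, so d = 0.31 × √6 = 0.759 for one method and 0.380 for the other.

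Simulation (200,000 trials) gives about 63% for vibration alone, tapping alone, both equally, and evenly spaced means. A significant omnibus result therefore does not distinguish these cases.

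**3. Familywise error with no true effect.** The contrasts are the two comparisons with control, each at 0.05 with pooled SD and 69 df, run only after a significant omnibus F:
- one time point: about 4%;
- either of the during and after scores may count: about 8% (7.8% at correlation 0.5, 8.2% at 0).

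With gating, the excess comes only from the unnamed time point.

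**4. Power per contrast, 24 per group, one time point.** For Dunnett the critical value is 2.258 (1.995 unadjusted). The noncentrality is d√(n/2) = 0.658 × √12 = 2.28, which gives 51%.

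| Pattern | Gated by omnibus F, 0.05 | Dunnett |
|---|---|---|
| One method, or both equally, d = 0.66 | about 54% | about 51% |
| Evenly spaced, d = 0.76 | about 61 to 62% | about 65% |
| Evenly spaced, d = 0.38 | about 24% | about 18% |

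For Dunnett, 80% power per contrast needs d of about 0.90. On scores rounded and bounded to 0–7 (assumed mean 4.5, SD 1.8), Holm-adjusted Mann-Whitney detects a single working method about 44 to 45% of the time.

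**The case against.** The strongest reply is that omnibus-first testing is a sound and common start for three groups, and that pairwise follow-up would be understood. Much of this stands. The omnibus test is not a wrong method. With three groups and one time point, contrasts run only after it is significant hold the familywise error, and their power is close to Dunnett's. The gap is the missing second step. The plan does not mention follow-up, so it cannot be presumed.

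It can also be said that the plural wording of the hypotheses fits an omnibus test. It does so loosely, but on that reading the two hypothesis pairs would be the same hypothesis stated twice.

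Three stronger readings are tempting and are not supported:
- **That the plan carries a 9% familywise error, or 16 to 17% over two time points.** Those rates belong to unadjusted contrasts run without the omnibus gate, a procedure that the documents nowhere state.
- **That each contrast keeps about 70% power.** That is Dunnett on the mean of all three measurements, with the full effect given to the score taken before the procedure. If only the during and after scores shift (d = 0.66, correlation 0.5), Dunnett power on that mean is about 35%.
- **That a significant omnibus test will often come with neither contrast significant.** If one method alone works, this happens in 7% of trials (contrasts at 0.05) to 13% (Dunnett). It is under 1% if both work equally. The size depends on the pattern of means, so the attribution problem is the firmer ground.

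**Conclusion.** The point holds as a gap between the hypotheses and the analysis. Followed as written, the plan tests neither H1a nor H1b separately, and it leaves the deciding pain score open. This conclusion comes from the text and needs no assumed numbers. It should be settled before data are seen, because a later choice of contrast method or time point could follow the results.

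The sizes are 63% omnibus power at one time point under every mean pattern examined, and familywise error of about 4% rising to about 8% if either the during or the after score may decide. They rest on 0.31 being Cohen's f and on normal data. The reproduction of 72 also needs the assumed correlation of 0.5. The documents give no effect-size type, SD or correlation, so the power figures are illustrations.

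A reader might infer that the sample size is miscalculated or that more infants are required. The documents do not support that: 72 is reproducible for an omnibus test over three measurements. What they lack is a statement of power for the two comparisons that the hypotheses name.

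**What to change.** Before data are seen:

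1. The investigator names one primary pain score and labels the other pain time points secondary. The stated purpose points towards the during-procedure NIPS score, but the choice is the investigator's.
2. Pre-specify two contrasts, vibration against control (H1a) and tapping against control (H1b). Either test each at 0.05 only after a significant omnibus test, which is valid for three groups at one time point and closest to the current text, or use Dunnett. Where the plan's non-normality rule applies, use Mann-Whitney tests gated by Kruskal-Wallis or adjusted by Holm.
3. Report each contrast with an effect estimate, a confidence interval matched to the method and, where an adjustment is used, the adjusted p-value.
4. State that the 0.80 power is reproduced only for an omnibus test over three measurements with an assumed correlation of 0.5. Restate power per contrast at 24 per group, with the assumed pattern of means.

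The cost is a few sentences and a lower stated power, as tabulated above. No new data are needed, and raising enrolment is not part of this fix.
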